10.8.4. Measurement Time Points

The time point will take place at study enrollment (pre-operative survey) and postoperatively at 3 months, 6 months, and 12 months.

10.8.5. Response Review

N/A

10.9. Secondary outcome measure: NAC vascularization

10.9.1. Relevant Subset

All patients (n=15).

10.9.2. Measurement Definition

NAC vascularization is defined by the presence of vascular tissue within the graft. Presence of bleeding from the graft following needle puncture using a lancet device will serve as the objective confirmation of vascularization.

Visual assessment using categories on a color chart (white, pink, light brown, blue, purple or black) will also be performed.

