2.6 Nipple Morphology and Pigmentation Considerations

When a NAC is recovered from a deceased donor, the areola diameter, nipple diameter, and nipple projection/height are measured. These characteristics and pertinent demographic information (age, race, BMI, etc.) will be tracked with each NAC as part of inventory. For consistency in the manufacturing process, the diameters of the areolas are uniformly sized to 2 cm, but the diameters (usually < 2 cm) and projections of the nipples themselves are not altered. We will categorize the NAC grafts as small, medium, and large on the basis of both nipple diameter and projection. In speaking with patients, it is clear that each has a unique preference for nipple size. When the physician places an order, the size preference will be matched from the inventory.

With respect to pigmentation, the process of decellularization generally removes all pigment (melanin) from the graft such that it appears as a pale white color just like Alloderm® or other acellular dermis products. In individuals with very darkly pigmented NACs, we sometimes see that a layer of melanin remains on the surface of the NAC graft after decellularization. In our studies of NAC graft engraftments on non-human primates whose skin lacks melanin, we saw that after healing occurred (6 weeks) the color of regenerated NAC was the same as the surrounding skin tissue, but with a pink hue due to blood vessel infiltration. On a microscopic level, what we saw is that cells infiltrated the graft and lined up along the basement membrane between the epidermis and dermis of the NAC graft and regenerated a new epidermis underneath the existing decellularized epidermis, sloughing off the decellularized epidermis. So, from these observations, we expect that regardless if melanin (only contained in the epidermis) remains on the surface of the graft or not after decellularization, it will be sloughed off during the healing process and the graft will take on the color of the patient's surrounding skin. Therefore, we expect that NAC grafts do not need to be matched for race. Since non-human primates do not have melanin, we could not ascertain from those studies whether the NAC grafts promote higher concentrations of melanocytes/melanin than normal skin and, therefore, result in a darker

pigmented NAC as compared to surrounding skin. If a patient is not satisfied with the color of their new NAC, tattooing can be performed after healing is complete.

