3.1. Inclusion Criteria

- 3.1.1. Women between 18 and 65 years old. No race-ethnic restrictions.
- 3.1.2. Patient has undergone uni- or bi-lateral autologous breast reconstruction a minimum of 3 months prior to enrolling in the study.
- 3.1.3. Patient agrees to sleep on her back until the graft(s) have healed (approximately 6 weeks).
- 3.1.4. Patient agrees to abstain from taking aspirin, drinking alcohol (>2 drinks per day), or consuming excessive amounts of caffeine (>300mg per day) until the graft(s) have healed (approximately 6 weeks).
- 3.1.5. Patient agrees to not undergo NAC tattooing until completing the study (approximately 12 months after engraftment).
- 3.1.6. Patient is able to understand and willing to sign an informed consent form.
- 3.1.7. Eastern Cooperative Oncology Group (ECOG) or Karnofsky Performance Status restrictions: N/A
- 3.1.8. Life expectancy restrictions: N/A
- 3.1.9. Requirements for organ and marrow function: N/A

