9. STUDY CALENDAR

	Screening	Day 0	Day 7 ^a	Day 14 ^a	Day 28 ^a	Day 42 ^a	Day 90 ^a	Day 180 ^a	Day 360 ^a	Personnel	Description
Informed Consent	X									Study Site Staff	
Height and Weight (for BMI)	X									Study Site Staff	
Medical History	X									Study Site Staff	
Vital Signs	X	X	X	X	X	X	X	X	Study Site Staff		Patient vital signs (heart rate, blood pressure, temperature) will be taken with the patient in a seated position and medications will be recorded.
Current Medications	X	X	X	X	X	X	X	X	Study Site Staff		
NACgraft Engraftment		X								Surgeon	
Surgical Time		X							Study Site Staff		Duration will be the time difference between initial incision of the wound bed (i.e. de-epithelialization) and placement of the final suture.
Discontinue Nipple Protector					X				Surgeon		The use of nipple protector bandage will be discontinued after 6 weeks ^b .
Photographs ^a	X	X	X	X	X	X	X	X	Study Site Staff		Digital photographs of each NACgraft will be taken for documentation and transmission to surgeon for specified endpoints.
Wound Healing			X	X	X	X	X	X	Surgeon		Visual inspection of the graft(s) will be conducted to assess the extent of NACgraft healing and identify any complications (e.g. necrosis, infection). Assessments will be performed by the study site Surgeon and, using the photographs. Wound healing will be assessed via the following metrics: epithelialization (0-100%), granulation (0-100%), ischemia/necrosis (0-100%), dehiscence (0-100%), and overall healing (0-100%).
Infection			X	X	X	X	X	X	Surgeon		Grafts will be assessed for infection via the following metrics: A) no infection; B) hyperemia (no infection); C) cellulitis (superficial infection); D) abscess or purulent infection.
Vascularity					X	X	X	X	X	Surgeon +	An assessment of blood flow to the NAC will be determined visually both by the surgeon and, using the digital photographs, by surgeon.. The NAC color will be graded as white, pink, light brown, blue, purple or black. In addition, each NACgraft will be pricked with a lancet/lancing device (the type used for obtaining fingerstick glucose measurement) in each quadrant of the areola, plus the nipple, for a total of 5 regions to determine vascularization. Lancing will be discontinued after the first post-operative visit demonstrating vascularity.
Graft Dimensions					X	X	X	X	Study Site Staff		Nipple projection/height and diameter will be measured with a Depth Gauge and Drill Gauge, respectively.

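### The colour chart for grading graft blood flow has nothing between light brown and black, so this supplementary grade may be invalid in women with medium- or dark-brown skin

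*Combined protocol and SAP*

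**What the plan says.** Section 10.9.2 defines vascularization as vascular tissue within the graft. Bleeding after a lancet prick "will serve as the objective confirmation of vascularization". Colour is a second assessment: "Visual assessment using categories on a color chart (white, pink, light brown, blue, purple or black) will also be performed". Section 10.9.3 repeats the same list for every follow-up visit named in Section 10.9.4: Days 28 and 42, then 3, 6 and 12 months.

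The Vascularity row of the study calendar (Section 9) gives the purpose of the visual grade, "An assessment of blood flow to the NAC will be determined visually", and again the same categories: "The NAC color will be graded as white, pink, light brown, blue, purple or black".

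Section 2.6 describes what colour to expect. After healing, "the graft will take on the color of the patient's surrounding skin", so the protocol does not plan to match grafts for race. For very darkly pigmented donors it notes that "we sometimes see that a layer of melanin remains on the surface of the NAC graft after decellularization", and expects that layer to be shed during healing. It also acknowledges a limit of the primate work, where the animals had no skin melanin: "we could not ascertain from those studies whether the NAC grafts promote higher concentrations of melanocytes/melanin than normal skin".

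On enrolment, Section 3.1 states: "No race-ethnic restrictions".

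**The concern.** A grading scale should have a category for every outcome the protocol itself expects. Here the expected healthy result is a graft the colour of the woman's own skin, and women of any skin tone may enrol. The chart admits pigment, since light brown is on it, but then jumps to black. An assessor looking at a well-healed medium- or dark-brown graft has no accurate choice. Two assessors, or one assessor at two visits, could reasonably choose differently.

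What is at stake is the visual blood-flow grade. In these women it would record pigment forced into an ill-fitting category, and a black entry could not be told apart from true discolouration. The pilot is meant to show that the data for a larger study can be collected (Sections 12.1 and 12.6.2), so a defect in the scale would be carried forward.

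**Working it through.** The documents state no figure to reproduce, and no power or sample-size formula applies. The check sets the sections side by side.

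1. **Categories.** Sections 9, 10.9.2 and 10.9.3 agree on six. One is a brown (light brown), and none lies between it and black. Because all three places agree, this is not a slip in one of them.
2. **Expected colour.** Section 2.6 expects a match to surrounding skin and leaves open whether the graft could end up darker than that skin. Either way, medium- and dark-brown grafts are foreseeable.
3. **Population.** Section 3.1 does not restrict race or ethnicity, and Section 3.2 has no exclusion by skin tone.
4. **Consequence of 1 to 3.** If the expectation in Section 2.6 is met in a woman with medium- or dark-brown skin, every available category misdescribes her graft.
5. **Link between colour and perfusion.** Section 2.6 reports a pink tint from vessel ingrowth in healed primate grafts. Those animals lacked melanin, so this observation does not show that colour tracks perfusion in pigmented skin.
6. **Donor melanin.** Grading begins at Day 28 (28/7 = 4 weeks). The primate healing point in Section 2.6 is 6 weeks (6 × 7 = 42 days). The Day 28 grade, and possibly the Day 42 grade, could therefore be taken before a residual donor layer has been shed. Later visits should be largely free of this. Section 10.9.4 lists no Day 0 grade, and no section asks for comparison with adjacent skin.
7. **Duration.** Section 10.9.3 continues colour grading at all five visits, while lancing stops once bleeding is shown.
8. **Analysis.** Section 12.5.2 summarises the data of Sections 10.3 to 10.9 and names weeks to vascularization. It does not name the colour grade, and no section states which colours count as perfused or ischaemic.

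**Size.** The skin-tone mix is not given, so the number of women affected lies between 0 and 15 of 15. Each one is 1/15 = 6.7% of the sample. With one grade per graft per visit, she contributes up to 5 grades if treated on one side and 2 × 5 = 10 if on both.

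**The case against.** The strongest reply is that colour is only an addition. Lancet bleeding is the stated confirmation, it does not depend on pigment, and no rule lets a later colour grade overturn it. A graft marked black has an imprecise colour label, not a wrong vascular status. That stands. A reader might infer that healthy grafts would be misclassified as not vascularized, or that weeks to vascularization would be biased. The documents do not support either reading, because no section maps any colour to vascular status.

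A reader might also infer false or missed ischaemia. Ischaemia/necrosis is rated separately by the surgeon on a 0-100% scale (Sections 9 and 10.2.3), with photographs, and that rating is not derived from the chart. Nor can it be said that colour is the only vascular measure once lancing ends. Section 10.1.3 lists vascularization among the surgeon's visual analogue ratings, which Section 10.1.4 runs until healing. Section 10.9.3 can also be read as stopping the lancet only in regions that have bled.

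Further points stand in part. Skin-matched colour is an expectation, and it concerns the healed graft, so the gap may not matter at Day 28. Light brown will suit some women. The calendar table is broken in extraction, and its photograph row may include Day 0, so a baseline image may exist even though no Day 0 grade is listed.

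None of this supplies the missing categories. The visual grade is collected to judge blood flow, runs to 12 months and falls within the data that Section 12.5.2 undertakes to summarise.

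**Conclusion.** The concern holds for the supplementary visual grade only. As written, the chart cannot correctly record a healthy medium- or dark-brown graft, so that grade may be invalid in women with such skin. Early grades may also reflect residual donor pigment. The lancet endpoint and the ischaemia/necrosis rating are untouched.

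The conclusion rests on two assumptions: that the colour match expected in Section 2.6 occurs at least in part, and that at least one woman with medium- or dark-brown skin enrols. The number affected cannot be estimated from the documents. This is a defect in a stated scale, cheap to correct, and worth correcting before the scale is reused in a larger study.

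**What to change.** In Sections 10.9.2 and 10.9.3 and the Vascularity row of the calendar:

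- add brown and dark brown to the chart;
- at each graded visit, also record graft colour relative to adjacent breast skin (same, paler, or darker/dusky);
- record the graft's own colour at Day 0, so that residual donor pigment can be recognised in the Day 28 and Day 42 grades.

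In Section 12.5.2, state that the visual grade will be tabulated descriptively by visit in relation to adjacent skin, with the Day 0 graft colour alongside. State also that lancet bleeding remains the vascularization endpoint and is not altered by the colour grade.

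The cost is revised protocol and form wording, one extra grade at Day 0, one extra field per visit and two more categories to tabulate. With 15 patients, the added categories will make some table cells sparse. That is a small price, since the table is descriptive.

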10.9.3. Measurement Methods

Presence of bleeding will be determined using a lancet device after cleaning the area with an alcohol swab. Results are reported for 5 quadrants (four corners plus central nipple). Once a quadrant shows bleeding, lancing is deferred for all future visits.

Visual assessment using categories on a color chart (white, pink, light brown, blue, purple or black) will be performed at all follow up visits specified in **Section 10.9.4**.

10.9.4. Measurement Time Points

Measurements will take place on day 28, 42, 3 months, 6 months, and 12 months.

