NAC (dcl-NHP-NAC group 1 and 2). Additional groups included native NAC (N-NAC), commercial control (Strattice, catalog No. 1016002; LifeCell Corporation, Branchburg, NJ), or surgery only (sham). Two dcl-NHP-NAC groups were included to reflect different decellularization batches. Tissue was harvested at days 2, 14, 21. Histology revealed greater neovascularization in dcl-NHP-NAC grafts as compared to the commercial control, with no observed biocompatibility issues. The grafts were then tested in an NHP model. Briefly, 18 dcl-NHP-NACs and two native host nipples were onlay grafted onto partial thickness wounds along the dorsal midline of rhesus macaques. Grafts were harvested at weeks 1, 3, and 6 for histological analysis. Results demonstrated successful neovascularization of the grafts that reached a steady state by 3 weeks post-engraftment. Furthermore, grafts showed complete re-epithelialization by 3 weeks, which remained unchanged through the end of the study.

This approach has now been replicated using human-derived NAC grafts implanted in an NHP model (manuscript in preparation). Results showed graft re-epithelialization, vascularization, and the presence of nerves within graft tissue by the 6-week timepoint, with preserved nipple projection. In summary, the above preclinical trials confirm the safety and clinical potential for this device to improve patient care.

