12.3. Descriptive Statistics and Exploratory Data Analysis

Descriptive statistics will be employed including t distribution for continuous variables, Poisson distribution for incidence rates, etc. and 95% confidence intervals will be applied for the measured primary and secondary outcomes.

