12.5.2. Analysis Plan

Secondary outcome data as described in **Section 10.3 – 10.9** will be characterized in terms of distributional characteristics such as the maximum, mean, median, and variation (as 95% confidence interval). Numerical scores (weeks to 50% and 75% graft healing, operative time, nipple projection, nipple diameter, NAC sensitivity, weeks to NAC vascularization, and LIKERT survey scores) will be characterized in terms of distributional characteristics such as the maximum, mean, median, and variation (as 95% confidence interval). Measurements reported as categorical variables (infection) will be characterized

as a percent.

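### Weeks to NAC vascularization is summarised by a mean and t interval, but lancet testing starts at Day 28, so the summary largely reflects the visit schedule

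*Combined protocol and SAP*

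**What the plan says.** Section 10.9.2 makes the lancet test the reference for this outcome: "Presence of bleeding from the graft following needle puncture using a lancet device will serve as the objective confirmation of vascularization". Section 10.9.4 sets the schedule: "Measurements will take place on day 28, 42, 3 months, 6 months, and 12 months". The Vascularity row of the study calendar (Section 9) carries five marks, consistent with Days 28, 42, 90, 180 and 360. Patients also attend on Days 7 and 14, but no vascularity test is listed for those visits. The calendar allows 4 days either side of each visit.

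Section 10.9.3 limits further testing: "Once a quadrant shows bleeding, lancing is deferred for all future visits". The calendar instead stops lancing after the first visit that shows vascularity.

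Section 12.5.2 includes "weeks to NAC vascularization, and LIKERT survey scores" among its numerical scores, to be summarised by maximum, mean, median and 95% confidence interval. Section 12.3 gives the method: "Descriptive statistics will be employed including t distribution for continuous variables, Poisson distribution for incidence rates". No section treats the time as left- or interval-censored, gives a value to a graft that never bleeds, or says how many of the five tested regions must bleed.

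On expected timing, Section 2.5 reports for primate-derived grafts: "Results demonstrated successful neovascularization of the grafts that reached a steady state by 3 weeks post-engraftment". Its next paragraph, on human-derived grafts placed in primates, says only that vascularization was present by 6 weeks.

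**The concern.** Because lancing stops once bleeding is seen, the first positive visit is the only lancet information on timing. It shows that vascularization happened at some point since the previous test or, for the first test, since surgery. Averaging those visit times as if they were onset times reports the assessment calendar as a biological duration. It also attaches a standard deviation and t interval that describe the gaps between visits.

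This matters because Section 12.6.2 gives, as one purpose of the 15 patients, preliminary estimates of the measures and their variability to help size a larger study. A standard deviation that is zero when all grafts pass the first test, and that jumps when one graft is late, serves that purpose poorly.

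**Working it through.** The plan gives no computed figure for this outcome, so there is nothing to reproduce.

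**Possible values.** Days divided by 7 (Section 10.9.4 and the calendar): 28/7 = 4.0, 42/7 = 6.0, 90/7 = 12.86, 180/7 = 25.71, 360/7 = 51.43 weeks. With the 4-day window the earliest test is Day 24, and 24/7 = 3.43 weeks.

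**Rounding up.** The recorded time can exceed the true onset by up to the gap since the last test:
- before Day 28: up to 28/7 = 4.0 weeks
- Day 28 to 42: up to 14/7 = 2.0 weeks
- Day 42 to 90: up to 48/7 = 6.9 weeks
- Day 90 to 180: up to 90/7 = 12.9 weeks
- Day 180 to 360: up to 180/7 = 25.7 weeks

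Onsets on Day 10 (1.4 weeks) and Day 27 (3.9 weeks) are both recorded as 4.0. An onset on Day 43 (6.1 weeks) is recorded as 12.9.

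**Planned summary in example patterns.** The number of grafts is not fixed: 15 patients with one or two grafts each give 15 to 30. If n − 1 grafts are positive at Day 28 and one at Day 90, the difference is d = 12.86 − 4.00 = 8.86 weeks. Then the mean is 4 + d/n, the SD is d/√n, the standard error is d/n, and the half-width is t × d/n.

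| Pattern | Mean | SD | 95% t interval |
|---|---|---|---|
| 15 grafts, all Day 28 | 4.00 | 0 | 4.00 to 4.00 |
| 15 grafts, one at Day 42 | 4.13 | 0.52 | 3.85 to 4.42 |
| 15 grafts, three at Day 42 | 4.40 | 0.83 | 3.94 to 4.86 |
| 15 grafts, one at Day 90 | 4.59 | 2.29 | 3.32 to 5.86 |
| 30 grafts, one at Day 90 | 4.30 | 1.62 | 3.69 to 4.90 |

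For the fourth row, 8.86/15 = 0.59 and the half-width is 2.145 × 0.59 = 1.27. For the last, 8.86/30 = 0.295 and the half-width is 2.045 × 0.295 = 0.60. The median is 4.0 in every row. These intervals treat grafts as independent, which two grafts in one woman are not.

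**Actual days instead of nominal weeks.** If all 15 grafts are positive at the Day 28 visit and visit dates spread uniformly over the 4-day window (an assumption), the average half-width is about 0.2 weeks. That width is only variation in appointment dates.

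**Sensitivity to true timing.** The documents give no onset times in women, so this rests on assumptions: 15 independent grafts, lognormal onset with log-SD 0.35, each onset rounded up to the next scheduled visit, 20,000 runs.

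| True mean (weeks) | Mean recorded | Interval covers true mean | Zero-width interval |
|---|---|---|---|
| 1.59 | 4.01 | 0% | 96% |
| 2.13 | 4.05 | 0% | 70% |
| 3.19 | 4.57 | 0% | 3% |
| 4.25 | 5.85 | 42% | 0% |
| 5.32 | 7.59 | 44% | 0% |

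The bias is upward in every row, and coverage is far below 95% even when onset is late. The problem does not depend on early vascularization.

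**The case against.** **Per-visit reporting.** The synopsis promises summary statistics at each time point, and Section 10.9.3 reports results by region, so a reader could probably see how many grafts bled at the first test. That is a fair point and makes the fix a small step, but the mean and t interval stay in Section 12.5.2.

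**An earlier rating.** Section 10.1.3 names a surgeon's visual analogue rating of vascularization within the healing assessment, which starts at Day 7. It is subjective, it is missing from the calendar's wound-healing metrics, and no rule turns it into weeks. It does not remove the floor.

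**Limited weight.** The outcome is secondary and descriptive. Section 12.7 does not list it among the criteria for a larger study, and Section 12.6.3 gives no historical comparison for it. This stands. A reader might infer that a future trial would be built on a wrong vascularization time, but the only link in the documents is the general purpose stated in Section 12.6.2.

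**Share of grafts at the floor.** A reader might infer from the 3-week primate figure that most grafts will be positive at the first test. The documents do not support that. The figure comes from histology of primate-derived grafts, and the human-derived grafts are described only at 6 weeks, which does not place onset before Day 28.

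**Grafts that never bleed.** A reader might infer that they drop out of the mean. The plan does not say so: Section 12.5.1 includes all participants under intention to treat. The gap is that it states no value for such a graft.

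**Conclusion.** The point holds as a defect in the planned summary of one secondary outcome. The plan takes the first positive visit as an exact time when it is only an upper bound, with a floor of 4.0 nominal weeks (3.4 at the edge of the window) and wide gaps after Day 42. The upward bias follows from the schedule alone. Its size depends on unknown true onset times: under the assumptions above, the recorded mean exceeded the true mean by between 1.4 weeks (4.57 − 3.19) and 2.4 weeks (4.01 − 1.59).

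The interval is no safer. On nominal weeks it can have zero width, or extend below any time the design can record: the lower limit of 3.32 is under the earliest possible 3.43. The milder 30-graft limit of 3.69 is below the nominal floor but not below the window-adjusted one. One late graft moves the mean by 0.6 weeks with 15 grafts and 0.3 with 30.

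The consequence is confined to the preliminary estimate and variability that the pilot is meant to supply. The point should be fixed, but no hypothesis test, primary outcome or go-forward decision rests on it.

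**What to change.** In Section 12.5.2:

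1. Replace the mean and t interval with the number and percent of grafts vascularized by Day 28, by Day 42 and by each later visit. Count grafts that never bleed as not vascularized.
2. Give 95% intervals that are exact at patient level, or graft-level intervals that allow for two grafts in one patient. As a guide to precision, exact limits are 78% to 100% for 15 of 15 patients and 68% to 99.8% for 14 of 15.
3. State whether one bleeding region or all five defines a vascularized graft. Reconcile Section 10.9.3 with the calendar on whether lancing stops by region or for the whole graft. The two choices must fit together: if testing of the whole graft ends at the first bleeding region, bleeding in all five cannot always be established.
4. If a time summary is kept, analyse it as interval-censored on actual days (0 to 28, 28 to 42, 42 to 90 and so on), with never-positive grafts right-censored at their last test.

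The cost is analysis wording and the reconciliation in item 3. No new visits or lancing are needed. What is lost is a single mean number of weeks.
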